9.1.1. Subject Disposition, Demographic and Background Characteristics

Subject disposition, demographic characteristics, and background variables will be summarized by study group.

9.1.2. Analysis of Efficacy

The primary analysis population will be the Intent-to-Treat (ITT) population, defined as all subjects randomized. A subset of efficacy analyses will be examined for the Efficacy Evaluable (EE) population defined as all subjects who were randomized, completed 14 days of study product use, had complete data at the Day 8 visit and did not have significant protocol deviations.

The primary analysis of all ophthalmic efficacy measures will be based on a single study eye for each subject. Each subject's study eye will be defined as the surgery eye.

The set of primary endpoints, using hierarchical statistical testing, is (1) the difference in the proportion of study eyes with complete resolution of anterior chamber cells (grade = 0) at postoperative Day 8 maintained through end of study and no need for rescue medication for KPI-121 0.25% QID compared to placebo; (2) the difference in the proportion of study eyes with complete resolution of anterior chamber cells (grade = 0) at postoperative Day 8 maintained through end of study and no need for rescue medication for KPI-121 1.0% BID compared to placebo;; (3) the difference in the proportion of study eyes with complete resolution of pain (grade = 0) at postoperative Day 8 maintained through end of study and no need for rescue medication for KPI-121 1.0% BID compared to placebo; and (4) the difference in the proportion of study eyes with complete resolution of pain (grade=0) at postoperative Day 8 maintained through end of study and no need for rescue medication for KPI-121 0.25% QID compared to placebo.

The following scoring scale for anterior chamber cells will be used:

- 0 = No cells seen
- 1 = 1 - 5 cells
- 2 = 6 - 15 cells
- 3 = 16 - 30 cells
- 4 = greater than 30 cells

The following scoring scale for ocular pain will be used:

- 0 = None
- 1 = Minimal
- 2 = Mild
- 3 = Moderate
- 4 = Moderately Severe
- 5 = Severe

If the two placebo groups demonstrate no statistically significant difference, they will be pooled for analysis.

Using the hierarchical testing scheme, the first test will be the difference in the proportion of study eyes with complete resolution of **anterior chamber cells** (grade = 0) at postoperative Day 8 between the pooled placebo control group and the KPI-121 0.25% QID group using the chi-squared statistic.

If this test is statistically significant at the two-sided $\alpha = 0.05$ level in favor of the KPI-121 0.25% QID group, then the difference in the proportion of study eyes with complete resolution of **anterior chamber cells** (grade = 0) at postoperative Day 8 between the pooled placebo control group and the KPI-121 1.0% BID group will be tested using the same statistic.

If this test is statistically significant at the two-sided $\alpha = 0.05$ level in favor of the KPI-121 1.0% BID group, then the difference in the proportion of study eyes with complete resolution of **pain** (grade = 0) at postoperative Day 8 between the pooled placebo control group and the KPI-121 1.0% BID group will be tested using the same statistic.

If this test is statistically significant at the two-sided $\alpha = 0.05$ level in favor of the KPI-121 1.0% BID group, then the difference in the proportion of study eyes with complete resolution of **pain** (grade = 0) at postoperative Day 8 between the pooled placebo control group and the KPI-121 0.25% QID group will be tested using the same statistic.

Secondary endpoints will be the proportion of study eyes with complete resolution (grade = 0) of anterior chamber cells (scale 0-4) and complete resolution (grade = 0) of pain (scale 0-5) at Day 8 and at Day 15.

Additional secondary endpoints are composite mean scores of anterior chamber cell and pain grades which will be summarized for each study group at each visit.

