8.5. RESCUE THERAPY

Any subjects not responding adequately to the study medication may be rescued and placed on alternate therapy at the Investigator's discretion at any time. The choice of rescue medication is at the Investigator's discretion. Any subject placed on rescue therapy will discontinue use of the study medication and continue study participation through Visit 7.

Rescued subjects will be considered treatment failures, but the need for rescue therapy will not be considered an AE. Rescued subjects experiencing an AE at the time of rescue will be followed through stabilization or resolution of the AE or the end of the study (whichever comes last).

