9.6. SUBJECTS TO BE INCLUDED IN THE ANALYSIS

Efficacy analysis will be performed for all randomized subjects (the ITT population) with at least one post-baseline (baseline = Visit 3) assessment. A subset of the efficacy analysis will be repeated using data from those subjects completing 14-days of study product use, fulfilling all study visits and achieving reasonable compliance with the study protocol (the EE population). AEs and other safety parameters will be analyzed for all randomized subjects receiving randomized study product (Safety population).

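### The Efficacy Evaluable set excludes any subject rescued before completing 14 days of study product, so the supportive analysis selects on a component of the primary endpoint

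*Combined protocol and SAP*

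**What the plan says.** The EE set is defined twice. Section 9.1.2 takes randomized subjects who "completed 14 days of study product use, had complete data at the Day 8 visit and did not have significant protocol deviations". Section 9.6 takes "those subjects completing 14-days of study product use, fulfilling all study visits" and adds reasonable compliance. The two wordings differ in other respects, but both carry the 14-day requirement and neither exempts rescued subjects.

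Section 8.5 sets the rescue rule: "Any subjects not responding adequately to the study medication may be rescued and placed on alternate therapy at the Investigator's discretion at any time". It continues: "Any subject placed on rescue therapy will discontinue use of the study medication and continue study participation through Visit 7". On outcome it says: "Rescued subjects will be considered treatment failures".

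The first primary endpoint in section 9.1.2 is complete resolution of anterior chamber cells "at postoperative Day 8 maintained through end of study and no need for rescue medication for KPI-121 0.25% QID compared to placebo". The other three primary endpoints carry the same rescue condition.

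The primary population is ITT. Neither 9.1.2 nor 9.6 puts a duration-of-use condition on ITT. EE is used for an unspecified subset of the efficacy analyses, and section 9.3 makes every p-value outside the hierarchical tests descriptive.

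**The concern.** A rescued subject may have taken every assigned dose up to rescue, followed section 8.5 to the letter, attended every visit and supplied complete Day 8 data. That subject still fails the EE definition, and the only reason is the 14-day clause. What triggered the exclusion is rescue, which is itself a way of failing the primary endpoint. The set is thus chosen partly on the outcome it is used to compare.

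Rescue is for subjects who do not respond adequately, so its frequency may differ between active and placebo. If so, EE removes different fractions of failures from the arms, and the comparison between arms is no longer protected by randomization. At stake is how agreement or disagreement between EE and ITT can be read. As the definition stands, either could arise from the pattern of rescue alone.

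**Working it through.** **Logic.** (a) EE requires 14 days of study product (9.1.2, 9.6). (b) Rescue ends study product and can happen at any time (8.5). (c) A rescued subject is a failure (8.5) and cannot meet a primary endpoint (9.1.2). From (a) and (b), a subject rescued before completing 14 days is outside EE. From (c), every subject removed this way is a non-responder on the primary endpoints.

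**The plan's own figure.** Section 9.2 gives 0.31 (active) v 0.14 (combined placebo), 134 per group, two-sided 0.05, and 91% power. Using the normal approximation without continuity correction:
- mean proportion = (0.31 + 0.14)/2 = 0.225
- null SE = √(2 × 0.225 × 0.775/134) = 0.0510
- alternative SE = √((0.31 × 0.69 + 0.14 × 0.86)/134) = 0.0499
- z = (0.17 − 1.96 × 0.0510)/0.0499 ≈ 1.40, so power is about 0.92

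The stated 91% is reproduced to within about one point, so these rates are a fair base for the illustration.

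**Effect on the EE rate.** Let p be an arm's planned responder rate and r the share rescued before completing 14 days. All responders are unrescued, so the exclusion leaves the numerator at 134p and cuts the denominator to 134(1 − r):

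EE rate = 134p / [134(1 − r)] = p/(1 − r)

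Example, placebo at r = 40%: 134 × 0.14 = 18.76 responders among 134 × 0.60 = 80.4 subjects, giving 0.233.

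The documents give no rescue rates. The shares below are assumptions, and all other reasons for EE exclusion are ignored.

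| Rescue active/placebo (assumed) | EE n active/placebo | EE rate active | EE rate placebo | EE difference |
|---|---|---|---|---|
| 0%/0% | 134/134 | 0.310 | 0.140 | 0.170 |
| 20%/20% | 107/107 | 0.387 | 0.175 | 0.212 |
| 10%/20% | 121/107 | 0.344 | 0.175 | 0.169 |
| 10%/30% | 121/94 | 0.344 | 0.200 | 0.144 |
| 10%/40% | 121/80 | 0.344 | 0.233 | 0.111 |

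**Where the direction changes.** Setting 0.31/(1 − r_active) − 0.14/(1 − r_placebo) = 0.17 and solving gives no net change at about 5%/10%, 10%/20% and 20%/36%. For a given active share, more placebo rescue than this shrinks the EE difference and less enlarges it.

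**If rescued subjects are kept as failures.** Rescue then removes nobody, and the contrast stays at 0.31 v 0.14 (difference 0.17) apart from other EE exclusions.

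**The case against.** The strongest reply is that nothing decisive rests on EE. ITT is primary, the sample size is not tied to EE, and EE p-values have no allocated alpha. That stands. It is why the table shows estimates only: power for an EE test would measure something the plan does not rely on.

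Second, the plan does not list which analyses use EE, and p/(1 − r) holds only where rescue means failure. The secondary endpoints (Day 8 and Day 15 resolution, mean grades) carry no rescue condition of their own. That also stands. For those endpoints rescued subjects are still dropped, but the formula does not give the size of the effect.

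Third, the rescue shares are assumed, and at 10%/20% the difference hardly moves. This is correct. A reader might infer that the exclusion dilutes the effect, or makes it seem to vanish among compliant subjects. The documents do not support a direction: with equal rescue the difference is inflated.

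Fourth, a reader might infer that every rescued subject is lost. That goes too far. Section 5.1.6 allows treatment at the end of Visit 6, and subjects first treated then may already have completed 14 days. The plan gives no working rule for completion, so cases near the Day 15 ± 1 visit are unclear.

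Fifth, no passage states what EE is for, and a pure completer set is a possible choice. But both definitions also contain compliance or deviation criteria, and nothing says that rescued failures are meant to be left out. A completer set would still need to be described as conditional on not being rescued.

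**Conclusion.** The point holds for the supportive analysis. Sections 8.5, 9.1.2 and 9.6, read together, remove from EE anyone rescued before completing 14 days, and they do so through a component of the primary endpoint. For the primary responder endpoints each arm's rate is raised by the factor 1/(1 − r). Across the assumed rescue shares shown, the planned difference of 0.17 becomes anything from 0.111 to 0.212. These figures rest on the section 9.2 rates, on assumed rescue before completing 14 days, and on no other EE exclusions. Neither the size nor the direction can be known from the documents.

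It would be wrong to read this as a threat to the primary conclusion: the ITT analysis is unaffected by the EE definition. The change is worth making because it is cheap and because, without it, a difference between EE and ITT cannot be interpreted.

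**What to change.** In both 9.1.2 and 9.6:

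1. Replace the 14-day requirement with: *study product used as assigned for 14 days or until rescue under section 8.5, whichever came first*.
2. State that rescued subjects otherwise free of significant deviations remain in EE as non-responders for the responder endpoints. Section 8.5 calls them failures but does not say they stay in EE, so this has to be written down.
3. State that rescue medication given under 8.5, even if listed in 6.2.2, is not by itself a significant protocol deviation for EE. The 6.2.2 list includes ocular corticosteroids and NSAIDs; without this sentence the same subjects could be excluded by the deviation criterion instead.

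The other differences between the two EE wordings can be reconciled in the same edit, but doing only that would leave this problem in place, since both contain the 14-day clause.

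The cost is a few sentences, settled before unmasking. No new data are needed, because section 8.5 already keeps rescued subjects in the study through Visit 7. The downside is that EE success rates will be lower in each arm than under the present definition, and EE will no longer be a pure completer set. No rescue, dosing or discontinuation rule changes.

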3.1.1.2. Secondary Efficacy Endpoints

- The proportion of study eyes with complete resolution (grade=0) of anterior chamber cells (scale 0-4) and complete resolution (grade=0) of pain (scale 0-5) at Day 8.
- The proportion of study eyes with complete resolution (grade=0) of anterior chamber cells (scale 0-4) and complete resolution (grade=0) of pain (scale 0-5) at Day 15.
- Mean grade of anterior chamber cells (scale 0-4) at Day 8.
- Mean pain grade (scale 0-5) at Day 8.
- Mean grade of anterior chamber cells (scale 0-4) at Day 15.
- Mean pain grade (scale 0-5) at Day 15.

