5.1.6. Visit 6: End of Study Product Use (Day 15 ±1 day)

The end of study product use visit will occur on Day 15 ±1 and the following will be performed/assessed:

- Use of any concomitant medications since the last visit
- Occurrence of any AEs since the last visit
- Collect used and unused study product
- UPT
- Subject-Rated Ocular Pain Assessment
- Snellen Distance VA by pinhole method
- Slit Lamp Biomicroscopy
 - Signs of anterior ocular inflammation (i.e., cell and flare grading)
 - Palpebral conjunctival erythema, corneal edema, hyphema, ciliary flush, bulbar conjunctival injection
- IOP Measurement
- Dilated Ophthalmoscopy
- Dosing compliance will be reviewed and assessed.

At the end of Visit 6, subjects with inflammation that has not resolved will be treated according to the Investigator's discretion. Regardless of treatment and after cessation of experimental medication, all subjects will be asked to return for follow-up on Days 17-19 for Visit 7.

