9.3. LEVEL OF SIGNIFICANCE

The primary assessment of the dose-response will be evaluated using a 5% level of significance using the hierarchical testing described in [Section 9.1.2 Analysis of Efficacy](#). All other reported p-values will be considered descriptive and hypothesis generating.

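### The four primary tests in Section 9.1.2 are worded on Day 8 clearance alone, while the primary response is defined as clearance kept to the end of the study without rescue

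*Combined protocol and SAP*

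**What the plan says.** **Definition.** The synopsis, Section 3.1.1.1 and the endpoint paragraph of Section 9.1.2 agree for all four primary endpoints (cells and pain, each active regimen). The eye must be at grade 0 at Day 8, and the result must be "maintained through end of study and no need for rescue medication for KPI-121 1.0% BID compared to placebo", with matching words for the 0.25% QID group.

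**Tests.** Later in Section 9.1.2 the hierarchy is set out step by step. Test 1 (cells, 0.25% QID) compares grade 0 "at postoperative Day 8 between the pooled placebo control group and the KPI-121 0.25% QID group using the chi-squared statistic". Tests 2 and 3 (cells, then pain, 1.0% BID) compare it "at postoperative Day 8 between the pooled placebo control group and the KPI-121 1.0% BID group will be tested using the same statistic". Test 4 (pain, 0.25% QID) follows the same form. None of the four mentions maintenance or rescue, and none refers back to the definition.

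**Related text.** Section 8.5 states: "Rescued subjects will be considered treatment failures, but the need for rescue therapy will not be considered an AE". Section 9.3 assigns the 5% level by "using the hierarchical testing described in" Section 9.1.2 and makes all other p-values descriptive. Section 9.2 gives 91% power for responder proportions of 0.31 and 0.14 with 134 per group, and does not say what a responder is.

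**The concern.** One section holds two descriptions of the same four tests. The definition carries a maintenance condition that the test paragraphs lack. Section 9.3 does not settle the matter, because it sends the reader to the section that contains both.

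These four tests carry the whole confirmatory claim, and a failed step ends the sequence. A programmer who follows the test paragraphs literally would count an eye that relapsed after Day 8 as a success, and so would analyse something other than the declared primary endpoint. If the question is noticed only after unmasking, whichever reading is chosen can be disputed. The stated power also belongs to one of the two responses, and the plan does not say which.

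**Working it through.** **1. How each kind of eye is classified**

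| Eye | By the definition | By the test paragraph |
|---|---|---|
| Grade 0 at Visits 5, 6 and 7, no rescue | responds | responds |
| Grade above 0 at Visit 5 | fails | fails |
| Rescued under Section 8.5 | fails | fails, through Section 8.5 |
| Grade 0 at Visit 5, above 0 at Visit 6 or 7, no rescue | fails | **responds** |

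Only the last row differs. Such eyes can be identified, because cells and pain are graded at Visits 5, 6 and 7 (Sections 5.1.5 to 5.1.7).

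**2. The plan's own power figure**

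Inputs from Section 9.2: p1 = 0.31, p0 = 0.14, n = 134 per group, two-sided alpha 0.05. The comparison of 134 with 134 assumes that the two placebo groups are pooled.

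Power = Φ[(p1 − p0 − 1.96·SE0) / SE1], where SE0 = √[2·p̄(1 − p̄)/n], SE1 = √[(p1(1 − p1) + p0(1 − p0))/n] and p̄ is the mean of p1 and p0.

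- SE0 = √(2 × 0.225 × 0.775 / 134) = 0.0510
- SE1 = √((0.2139 + 0.1204) / 134) = 0.0499
- Power = Φ[(0.17 − 0.1000) / 0.0499] = Φ(1.40) = 0.919

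This agrees with the stated 91% to within a point.

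**3. If 0.31 and 0.14 are Day 8 rates**

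The sustained rate is the Day 8 rate × (1 − relapse share). The shares are assumptions; the plan gives none.

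| Relapse among Day 8 responders | Sustained rates | Power |
|---|---|---|
| 0% both arms | 0.310 v 0.140 | 0.92 |
| 10% both | 0.279 v 0.126 | 0.88 |
| 20% both | 0.248 v 0.112 | 0.83 |
| 30% both | 0.217 v 0.098 | 0.77 |
| 50% both | 0.155 v 0.070 | 0.60 |
| 20% active, 10% placebo | 0.248 v 0.126 | 0.73 |
| 10% active, 30% placebo | 0.279 v 0.098 | 0.97 |

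**4. If 0.31 and 0.14 are sustained rates**

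The Day 8 rate is the sustained rate / (1 − relapse share). With equal relapse of 10%, 20% and 30% the Day 8 rates are 0.344 v 0.156, 0.387 v 0.175 and 0.443 v 0.200. The Day 8 test then has power 0.95, 0.98 and 0.99. Its power rises, but it answers a different question.

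**5. Could the choice change a result?**

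Chi-squared without continuity correction, 134 per group, placebo v active. Expected counts are 0.14 × 134 ≈ 19 and 0.31 × 134 ≈ 42, which give p = 0.0008.

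*Counts taken as sustained; the Day 8 test adds relapsed eyes back:*
- 10% relapse in both arms: 21 v 47, p = 0.0003.
- 9 placebo and 0 active eyes added: 28 v 42, p = 0.052. This means 9/28 = 32% of placebo Day 8 responders relapsed and no active ones.
- 18 and 10 added: 37 v 52, p = 0.052. This means 18/37 = 49% v 10/52 = 19% relapsed.

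*Counts taken as Day 8; the sustained test removes relapsed eyes:*
- 20% in both arms: 15 v 34, p = 0.003.
- 50% in both arms: 10 v 21, p = 0.036.
- 60% in both arms: 8 v 17, p = 0.059.

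**The case against.** The best answer is that the test paragraphs are shorthand. The full definition appears three times without variation. The tests follow it in the same section and take the endpoints in the same distinctive order. No other primary endpoint is declared. This reading is plausible, and probably what was meant. It does not remove the need for the edit, because the short form is written out four times in the only paragraphs that fix the statistic and alpha.

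A reader might go further in three ways that the documents do not support.

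- *That shorthand is ruled out.* Section 3.1.1.2 lists a secondary endpoint ending "complete resolution (grade=0) of pain (scale 0-5) at Day 8", and Section 9.1.2 asks the efficacy-evaluable set for subjects who "completed 14 days of study product use, had complete data at the Day 8 visit and did not have significant protocol deviations". Neither is decisive. A literal reading would make the primary tests nearly repeat a declared secondary endpoint, which favours the full definition. The secondary endpoint can also be read as cells and pain jointly. Section 9.6 describes the evaluable set as attending every study visit, which suits a maintained endpoint.
- *That eyes treated at Visit 6 form a second group in conflict.* Section 5.1.6 says: "At the end of Visit 6, subjects with inflammation that has not resolved will be treated according to the" investigator's judgement. It does not call this rescue. If it is rescue, Section 8.5 makes the eye a failure under either text. If it is not, an eye still at grade 0 on the tested measure can respond under either. An eye whose tested grade has risen is simply a relapse, already covered.
- *That the trial's result is likely to turn on this.* The counts above show that losing significance takes a large difference in relapse between arms, or about 60% relapse in both.

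**Conclusion.** The inconsistency is real in all four tests and is limited to the maintenance condition. Followed literally, the confirmatory tests would count unrescued relapses after Day 8 as successes, contrary to the declared primary endpoint.

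Its size depends on relapse rates that the plan does not give. With small, equal losses both versions reach significance at the assumed rates. If the Section 9.2 rates are for Day 8, equal relapse of 10% to 20% costs roughly 4 to 9 points of power. If they are sustained rates, the planned power stands for the defined endpoint, and the Day 8 test would have 95% to 99% power at 10% to 30% equal relapse, for a different endpoint. These figures assume pooled placebo and 134 per comparison group.

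This is a drafting inconsistency that should be corrected before unmasking. It does not show that the design is unsound.

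**What to change.** In each of the four test paragraphs of Section 9.1.2, replace the Day 8 phrase with: *the primary response defined above (grade 0 at Day 8 and at every later visit through Visit 7, with no rescue under Section 8.5)*. This also ties the end of the study to a named visit. In Section 9.2, state whether 0.31 and 0.14 are rates for that response. Day 8 clearance alone stays where it is, among the secondary endpoints.

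Whether treatment started at the end of Visit 6 counts as rescue is a separate endpoint decision for the sponsor. It should not be settled through this edit: counting it as rescue would fail eyes that were pain-free at every visit because their inflammation was treated.

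The cost is one amendment to wording. The grades needed are already collected at Visits 5, 6 and 7, so no visits, subjects or data are added. If the Section 9.2 rates prove to be Day 8 rates, the sample size should be rechecked against the sustained response.

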3. TRIAL DESIGN

3.1. ENDPOINTS

3.1.1. Efficacy Endpoints

3.1.1.1. Primary Efficacy Endpoints

The primary endpoints of this study will be evaluated using hierarchical statistical testing in the following sequence:

- (1) the difference in the proportion of study eyes with complete resolution of anterior chamber cells (grade = 0) at postoperative Day 8 maintained through end of study and no need for rescue medication for KPI-121 0.25% QID compared to placebo;
- (2) the difference in the proportion of study eyes with complete resolution of anterior chamber cells (grade = 0) at postoperative Day 8 maintained through end of study and no need for rescue medication for KPI-121 1.0% BID compared to placebo;
- (3) the difference in the proportion of study eyes with complete resolution of pain (grade = 0) at postoperative Day 8 maintained through end of study and no need for rescue medication for KPI-121 1.0% BID compared to placebo; and
- (4) the difference in the proportion of study eyes with complete resolution of pain (grade = 0) at postoperative Day 8 maintained through end of study and no need for rescue medication for KPI-121 0.25% QID compared to placebo.

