4.3. RANDOMIZATION CRITERIA

To qualify for randomization at Visit 3 (Postoperative Day 1), a subject must:

1. Have undergone routine, uncomplicated cataract surgery (e.g., phacoemulsification with posterior chamber IOL implantation, not combined with any other surgery).
2. Have \geq Grade 2 anterior chamber cells.
3. Continue to meet inclusion/exclusion criteria with respect to current ocular and medical conditions ([Section 4.1](#) and [Section 4.2](#)), and must not have taken prohibited medications ([Section 6.2.2](#)).

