5.1.3. Visit 3: Randomization Visit (Day 1)

The randomization visit will occur 1 day after Visit 2/Surgery Visit. This visit should be scheduled in the morning (if possible) to allow for administration of either BID or QID dosing of study product during the day for eligible subjects.

Eligible subjects who meet the randomization criteria ([Section 4.3](#)) will continue in the study. The following will be performed/assessed:

- Use of any concomitant medications since the last visit
- Occurrence of any AEs since the last visit (**NOTE:** Expected changes or the presence of inflammation resulting from routine uncomplicated cataract surgery will not be captured as AEs.)
- Subject-Rated Ocular Pain Assessment
- Snellen Distance VA by pinhole method
- Slit Lamp Biomicroscopy
 - Signs of anterior ocular inflammation (cell and flare grading)
 - Palpebral conjunctival erythema, corneal edema, hyphema, ciliary flush, bulbar conjunctival injection
- IOP Measurement

NOTE: All ocular assessments must be performed in each eye.

- Upon verification of study eligibility ([Section 4.3](#)), all eligible subjects will be randomized to receive four times per day dosing of either 0.25% KPI-121 drug product or Placebo A **OR** two times per day dosing of either 1.0% KPI-121 drug

product or Placebo B. The following will be performed for all randomized subjects:

- The first dose of double-masked study product will be administered in the clinic under the supervision of designated study personnel. Prior to administration of study product, subjects will be reminded on the proper method for instillation including but not limited to shaking study product bottle prior to each instillation. Since subjects will receive one (1) dose of study product in the clinic, they will self-administer at most three (3) additional doses of study product on the first day if assigned to the QID groups or one (1) additional dose of study product if assigned to the BID dosing group.
- Assess the occurrence of any AEs after study product administration
- Study product kits and instructions for administration will be dispensed
- Subjects will be scheduled to return for Visit 4 on Day 4 \pm 1 day.

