APPENDIX 2: SUBJECT-RATED OCULAR PAIN ASSESSMENT

In the clinic, subjects will be handed the Subject-Rated Ocular Pain Assessment to subjectively rate their pain at Visit 3 to 7. The grading scale for pain to be used will be as follows:

- | | |
|------------------------|---|
| 0 = None: | Absence of positive sensation. |
| 1 = Minimal: | Presence of mild sensation or discomfort typical of postoperative surgery (e.g., diffuse or focal foreign body sensation, mild transient burning or stinging, etc.) |
| 2 = Mild: | Mild, tolerable aching of the eye. |
| 3 = Moderate: | Moderate or more prolonged aching sufficient to require the use of over the counter (OTC) analgesics (e.g. acetaminophen). |
| 4 = Moderately Severe: | More prolonged aching requiring the use of an OTC analgesic other than acetaminophen. |
| 5 = Severe: | Intense ocular, periocular or radiating pain (e.g. constant or nearly constant sharp stabbing pain, throbbing or aching, etc.) requiring prescription analgesics. |

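### Primary tests 3 and 4 count eyes with no pain at Visit 3 as resolved, and the unadjusted chi-squared test leaves out the Visit 3 pain grade

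*Combined protocol and SAP*

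**What the plan says.** - **Endpoint.** Section 3.1.1.1 defines the pain response for tests 3 and 4 as "complete resolution of pain (grade = 0) at postoperative Day 8 maintained through end of study and no need for rescue medication". It places no condition on the grade at Visit 3.
- **Entry.** Section 4.3 requires at least "Grade 2 anterior chamber cells" on the day after surgery. It sets no pain threshold.
- **Population.** Section 9.1.2 uses the "Intent-to-Treat (ITT) population, defined as all subjects randomized".
- **Test.** Section 9.1.2 names the chi-squared statistic for test 1 and carries it forward. For test 4 the comparison "between the pooled placebo control group and the KPI-121 0.25% QID group will be tested using the same statistic". No stratum or covariate is named.
- **Availability of the Visit 3 grade.** In Appendix 2, subjects "subjectively rate their pain at Visit 3 to 7", on a scale that starts at 0 for none. Section 5.1.3 lists the pain rating ahead of randomization and then says: "The first dose of double-masked study product will be administered in the clinic under the supervision of designated study personnel". Section 9.6 calls Visit 3 the baseline ("with at least one post-baseline (baseline = Visit 3) assessment").
- **Stated use of that grade.** The only one is in section 9.1.2, among composite mean scores of cell and "pain grades which will be summarized for each study group at each visit".

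**The concern.** Cells and pain are treated alike, but only cells have an entry threshold. Every randomized eye has cells to clear, so grade 0 at Day 8 means that cells resolved. For pain, grade 0 at Day 8 mixes eyes whose pain went away with eyes that had none on the day after surgery. No planned analysis separates the two.

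Two things are at stake:

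1. **Meaning.** The sponsor is developing the product for postoperative inflammation and pain (section 1). A rate labelled as resolution cannot be read that way if an unknown part of it is pain that was never there.
2. **Efficiency.** Visit 3 pain probably predicts Day 8 pain. Leaving a prognostic baseline value out of a confirmatory test gives up power, and failure of test 3 blocks test 4.

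**Working it through.** **Step 1: the plan's own figure.** Section 9.2 gives 0.31 against 0.14, 134 per group, two-sided 5%, 91% power. With mean rate 0.225:

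Φ{[0.17 − 1.96·√(2·0.225·0.775/134)] / √[(0.31·0.69 + 0.14·0.86)/134]} = Φ(1.40) = 91.9%.

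The figure reproduces. Section 9.2 does not say whether these rates refer to cells or to pain.

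**Step 2: assumed inputs.** The documents give no pain rates, so all of these are assumptions:
- share f of eyes at pain grade 0 at Visit 3: 5%, 10%, 20%, 30%, 40%;
- painful eyes over grades 1 / 2 / 3 or more: 40/35/25, 50/30/20 or 60/30/10%;
- placebo response by Visit 3 grade 0 / 1 / 2 / 3 or more: set A 0.65, 0.35, 0.22, 0.10; set B 0.80, 0.30, 0.20, 0.10;
- odds ratio 1.75, 2.0 or 2.5, either in grades 1 and above only or in all grades;
- 134 per arm, from section 9.2.

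**Step 3: how many placebo responders had no pain to resolve.** With q0 the response of pain-free eyes and q1 the mean response of painful eyes, the fraction is f·q0 / [f·q0 + (1 − f)·q1].

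Example, f = 0.30, split 40/35/25:
- Set A: q1 = 0.4·0.35 + 0.35·0.22 + 0.25·0.10 = 0.242, so 0.195 / (0.195 + 0.169) = 54%.
- Set B: q1 = 0.215, so 0.240 / (0.240 + 0.1505) = 61%.

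Over both sets and all splits:

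| Pain-free share f | Fraction of placebo responders |
|---|---|
| 5% | 10.7–16.4% |
| 10% | 20.2–29.3% |
| 20% | 36.2–48.2% |
| 30% | 49.3–61.5% |
| 40% | 60.2–71.3% |

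**Step 4: power with and without the Visit 3 grade.** The comparison is the planned chi-squared test against a Mantel-Haenszel risk difference with Sato variance, strata 0 and 1 or more.

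By hand for set A, f = 0.30, split 40/35/25, odds ratio 2.0 in painful eyes only:
- The odds ratio turns 0.35, 0.22, 0.10 into 0.519, 0.361, 0.182, a mean of 0.379 in painful eyes.
- The overall rates are 0.364 and 0.460, a difference of 0.096.
- Crude SE = √[(0.460·0.540 + 0.364·0.636)/134] = 0.0598. Power ≈ Φ(0.096/0.0598 − 1.96) ≈ 36%.
- Stratified SE = √{[0.30·2·0.65·0.35 + 0.70·(0.379·0.621 + 0.242·0.758)]/134} = 0.0566. Power ≈ Φ(0.096/0.0566 − 1.96) ≈ 40%.

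The difference being estimated is the same; only its standard error shrinks. Simulation (40,000 trials per scenario, significant in favour of the drug) for the same share, split and odds ratio:

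| Drug effect | Set | Chi-squared | Stratified |
|---|---|---|---|
| Painful eyes only | A | 37.0% | 39.7% |
| Painful eyes only | B | 34.4% | 41.7% |
| All eyes | A | 63.8% | 69.7% |
| All eyes | B | 51.0% | 63.9% |

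Gains over all scenarios, in points of power:

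| Drug effect | f = 5–10% | f = 20–40% |
|---|---|---|
| Painful eyes only | 0.4 to 6 | 1 to 11 |
| All eyes | 0.4 to 7 | 2 to 16 |

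**Step 5: downside and validity.**
- If baseline pain is weakly prognostic (0.45, 0.35, 0.30, 0.25) or not prognostic (0.35 throughout), power changes by −0.9 to +0.7 points.
- Two-sided type I error is 4.8–5.5% for chi-squared and 5.0–5.3% for the stratified test.

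**Step 6: with the multiple imputation of section 9.4.** This used 5% or 10% missing outcomes, missingness depending on Visit 3 grade, 20 imputations by arm and stratum, and Rubin's rules. The simulation was smaller: 6,000 trials per power scenario and 20,000 for type I error. Type I error is 4.9–5.6%. Gains over an imputed crude test are 1 to 11 points (painful eyes only) and 1 to 14 points (all eyes).

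**The case against.** The strongest reply is that nothing here is a statistical error. The chi-squared test in all randomized subjects is valid, and the endpoint's operational definition is stated wherever it appears. A pain-free eye does not count automatically either, since later pain or rescue makes it a failure. All of that stands, and it limits the point to labelling and efficiency.

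The size is also open to challenge:
- **High shares may be unrealistic.** Appendix 2 reserves grade 0 for no sensation at all, and grade 1 already covers ordinary postoperative discomfort. On the day after surgery, 20% to 40% at grade 0 may be too many. The 5% to 10% rows are there for this reason, and their gains are at most 7 points.
- **The 0.14 placebo rate.** The assumed sets imply about 24% to 47% placebo response. If 0.14 in section 9.2 was also meant for pain, shares of 30% to 40% are impossible, because pain-free eyes alone would contribute 0.30·0.65 = 0.195 to 0.40·0.80 = 0.32. This caps the share but does not help the label. At 5% to 10% pain-free they would contribute 0.0325 to 0.08, which is 23% to 57% of a 0.14 response rate.
- **The gate.** Test 3 is reached only after tests 1 and 2 succeed, in about 87% of trials at the section 9.2 rates. If pain and cell results are independent, unconditional gains are about one-eighth smaller.

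Finally, stratifying does not stop pain-free eyes from counting as responders, and it gives one hierarchy two methods. Both are true. The table, the supportive analysis and the wording deal with meaning; the stratified test deals with power only. The reference to background variables in section 9.1.1 does not name pain and would not link Visit 3 pain to response.

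**Conclusion.** The concern holds. As written, eyes without pain at Visit 3 can be reported as resolved, and no planned analysis shows how many were. This follows from the text and needs only that some eyes start at grade 0. The share of placebo responders affected and the power gained, tabulated above, rest wholly on assumed pain rates.

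The planned test is not invalid. No loss from dilution is claimed, because that depends on the unknown pain-free share and stratifying would not remove it. This is a change the sponsor should make, not one without which the trial fails. Confidence in the size is medium.

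**What to change.** 1. **Section 9.1.2, tests 3 and 4.** Make the primary analysis a Cochran-Mantel-Haenszel type comparison with two strata, Visit 3 pain grade 0 and 1 or more. Fix the split now, use it for both tests and allow no data-driven collapse. State that the single primary p-value and the 95% CI come from the Mantel-Haenszel weighted risk difference with Sato variance, combined over the section 9.4 imputations by Rubin's rules. Include arm and Visit 3 pain grade in the imputation model. Rescued subjects are non-responders under section 8.5 and are not imputed. A subject with no Visit 3 grade goes into the 1-or-more stratum.
2. **Added outputs.** Prespecify a table of response by Visit 3 pain grade and arm, and a supportive analysis of tests 3 and 4 in subjects with Visit 3 grade 1 or more.
3. **Wording.** In the synopsis, 3.1.1.1 and 9.1.2, describe endpoints 3 and 4 as absence of pain (grade 0) at Day 8, maintained through end of study, without rescue.

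Eligibility, visits, sample size, test order and tests 1 and 2 do not change. The cost is wording and programming, since the grade is already collected, plus a sentence in 9.2 saying that its power figure describes the chi-squared comparison. If Visit 3 pain proves not prognostic, the loss is at worst 0.9 points of power for this test, against 1.3 for a two-stratum CMH test and 1.9 with four strata. All of it must be settled before unmasking. If the sponsor keeps chi-squared as primary, items 2 and 3 alone still close the gap in meaning.
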